#### SOP-1 Approval of centres to join the trial and access trial drugs

One National Co-Principal investigator will work together to get all necessary approvals rapidly, to select as potential collaborating research centres and/or local hospitals that already have, or are expected soon to have, substantial numbers of outpatient and or inpatient admissions for Monkeypox, and to facilitate local ethical approval on behalf of willing local collaborators. The following steps should ensure the trial can start promptly in each collaborating hospital. They should happen in parallel and not in sequential fashion.

Step	What?	Who?	How?	Remarks
1	Officially confirm interest to participate	To be defined for each country	Communication to trial secretariat	
2	Appoint one National Co- Principal investigator	A leading clinical investigator	Communication to trial secretariat	These National Co- Principal investigator should both be senior
3	Identify which research centres and/or local hospitals will have substantial numbers and will collaborate	One National Co- Principal investigator	Communication to trial Secretariat	Selected centres and hospitals should have basic GCP knowledge
4	Facilitate Approval - or not - by national authority and local ethics committees	National Co- Principal investigator	High-level national decisions, not just local applications by each collaborator	No modification of the protocol is possible, as very large numbers of hospitals are involved. Add on studies can be considererd
5	Establish which study drugs are available in each location	National Co- Principal investigator	Bilateral interactions	Trial secretariat will facilitate study drug provision where this is needed
6	Facilitate import permits for study drugs, as pertinent	National Co- Principal investigator	Depends on national guidelines and regulations	After permits for initial amounts, resupply will depend on entry rate
7	Set up personnel and logistics for study implementation	Appoint small central administrative staff for the Clinical National Representative	Make use of existing p.a. and other staff of known reliability to disseminate study	Local centres will need help on approvals, drug supplies, getting going, and maximising accrual
8	Within research centres and/or local hospitals, move quickly into rapid recruitment	Lead doctor and lead pharmacist motivate and train colleagues	Local leads explain and discuss study with colleagues	Local leads motivates & ensures full compliance, rapid entry & discipline

#### **CORE** protocol

#### **Standard Operating Procedures**

#### SOP-2 Access to global enrolment and randomization center

To facilitate collaboration even in overloaded hospitals, patient enrolment and randomisation (via a cloud-based GCP-compliant platform) and all other trial procedures are greatly simplified.

Within each country, the national co-ordinator invites selected hospitals and helps them get ethical and regulatory approval and study drugs then patient entry can begin. Access is via the study website XXXXXXXXXXX.

Each doctor has access to the platform using an individual secured password. A study ID for the patient is then generated and displayed.

**Eligibility:** Adults and children with laboratory-confirmed (PCR) monkeypox illness of any duration (provided that the patient has at least one active, not yet scabbed, lesion), and, have no contra-indication to potentially study drug.

**Consent:** The study website XXXXXXXXXXX has printable patient information in some languages. Once the information has been explained to patients, obtaining consent takes only a few minutes. An electronic image of the signature page is kept (or, if national regulations forbid this, a copy of the consent must be kept in the file), and the printed information and original consent stays with the patient or legal representative.

#### Data collected electronically immediately before randomisation:

- o Country, geographic region of residence, hospital and randomizing doctor
- Confirmation that informed consent was obtained from the patient (or a surrogate/ representative)
- Age, sex and (yes/no): HIV, TB, malaria, hypertension, diabetes mellitus, asthma, hepatitis, hyperlipidemia, cancer, heart failure, renal disease, liver disease, chronic obstructive pulmonary disease (COPD), COVID-19, neoplasm, obstructive sleep apnea, obesity, immunosuppressive disorder other than HIV, sickle cell anemia, concurrent bacterial infections such as urinary tract, ear nose and/or throat, pulmonary, central nervous system, skin or gastrointestinal infection, bacteremia/sepsis or other.
- Date of onset of symptoms, date of hospitalization, and (yes/no) current/planned use of a few drugs
- Monkeypox lesions status (yes/no): at least one active, not yet scabbed, monkeypox lesion, other.
- o Current symptoms (yes/no): nausea, vomiting, abdominal pain, anorexia, cough, lymphadenopathy, dysphagia, fever, headache, ocular lesions, and buccal ulcers.
- Smallpox vaccination status (yes/no) or presence of vaccination scar (yes/no).
- Risk factors for monkeypox infection (yes/no): recent contact with known monkey pox case, type of contact, residing or visiting an area with an active monkey pox outbreak, animal handling.

**Trial entry; randomization:** A participant will be considered enrolled beginning from when the informed consent form is signed and randomization to an assigned treatment has occurred. Once enrolled, study drug administration will begin according to study group assignment. Participants will be randomized to one of the experimental treatments (k in number) for which they are eligible (no specific exclusion criteria) or to one of the placebos that correspond (in appearance, dosing interval, and route of administration) to each of those treatments. The randomization ratio will ensure that

participants have the same chance of receiving a placebo as they have of receiving each individual treatment for which they are eligible. All participants will also receive local SOC that is standardized at each site according to local/site guidance.

#### **CORE** protocol

#### **Standard Operating Procedures**

#### **SOP-4 Pharmacy manual for XXXXXX**

#### 1. Drug product

XXXXXXXXX

#### 2. Drug receipt

XXXXXXX

#### 3. Storage and handling

Acquisition: Study treatment and placebo will be shipped to the study site where administration will take place, in compliance with all applicable transport guidelines.

Accountability: The study pharmacist will be responsible for maintaining an accurate record of the study arm codes, inventory, and an accountability record of study agent supplies.

#### 4. Dose preparation

XXXXXX

#### 5. Disposition of unused product

XXXXXX

#### 6. Maintenance of inventory logs

XXXXXX.

#### 7. Emergency contact

XXXXXX.

#### **SOP-7 Reporting of main outcomes**

To facilitate collaboration even in health facilities that have become overloaded, patient enrolment and randomization (via the internet) and all other trial procedures are greatly simplified, and no paperwork at all is required.

Withdrawal from the treatment that was randomly allocated at study entry need not imply withdrawal from information on outcome in hospital being reported to the trial database at the end of the study follow up. But, if the patient (or a legal representative) decides the patient will withdraw and that no further data will be sent to the TRIAL SPONSOR study office, then only the date of withdrawal will be reported; no further information will be given, unless an adverse drug reaction report is legally required.

At discharge or death, the study doctor will log into the study website and enter:

When patients die or are discharged, follow-up ceases and it is reported:

- Which study drug was given (and for how long?)
- Which of a few selected other drugs were given (and for how long?)
- What treatment support was given

Patient information will be encrypted and held securely by the at the cloud database.

Those analysing it will use only anonymized data, and no identifiable patient details will be released to any unauthorized third party. Patient confidentiality will be maintained when study results are disseminated.

#### **SOP-8 Safety Reporting**

The principles of ICH E6 (R1) GCP require that both investigators and Sponsors follow specific procedures when notifying and reporting adverse events or reactions in clinical trials. These procedures are described in this section of the protocol.

Standard Operating Procedure (SOP) outlining the reporting procedure for clinicians will be provided on the reverse of the SAE form. An SOP will also be available as part of the Trial Specific SOPs which will outline the reporting procedure for the Trial Co-ordinating Centre.

#### **Definitions**

The definitions of the EU Directive 2001/20/EC Article 2 (and subsequent revised version CT3) based on the principles of ICH E6 (R1) GCP and any local requirements apply to this trial protocol. These definitions are given in Table 1

Table 1: Definitions of Adverse Events

TERM	DEFINITION
Adverse Event (AE)	Any untoward medical occurrence in a patient or clinical trial subject administered a medicinal product and which does not necessarily have a causal relationship with this treatment.  An adverse event (AE) can therefore be any unfavourable and unintended sign (including an abnormal laboratory finding), symptom, or disease temporally associated with the use of a medicinal (investigational) product, whether or not related to the medicinal (investigational) product
Adverse Reaction (AR)	All untoward and unintended responses to an investigational medicinal product related to any dose administered
Death	Deaths are always SAEs. For fatal cases, the Investigator (and/or the designees) will have to fill-in an "SAE" CRF form, an "SAE" form which will be immediately notified by the Investigator to the sponsor or its designees). In case "death" is the only information available at the time of the SAE notification, it has to be reported as such. Nevertheless, the cause of death should be further investigated since death has to be considered as an outcome and not as an event.
Life threatening	Life threatening refers to an event/reaction in which the subject is at risk of death at the time of the event/reaction; it does not refer to an event/reaction that hypothetically might have caused death if more severe.

Important Medical Event (IME)	Any event that might not be immediately life threatening or result in death or hospitalization but might jeopardize the subject or might require intervention to prevent one of the other outcomes listed above.	
Serious Adverse Event or Serious Adverse Reaction (SAE or SAR)	Respectively any adverse event, adverse reaction that: 
 
results in death
 
is life-threatening
 
requires hospitalisation or prolongation of existing hospitalisation
 
results in persistent or significant disability or incapacity
 
is a congenital anomaly or birth defect
 
other medically important/clinically significant events
 
	
Severity (AE grading scale to be defined into the protocol)	Intensity of any adverse event from grade 1 to 5. 1=mild 2=moderate 3=severe 4=life threatening 5=death	
Suspected Unexpected Serious Adverse Reaction (SUSAR)	A serious adverse reaction, the nature and severity of which is not consistent with the information about the medicinal product in question set out:  in the case of a product with a marketing authorisation, in the summary of product characteristics (SmPC) for that product  In the case of any other investigational medicinal product, in the investigator's brochure (IB) relating to the trial in question.	
Unexpected Adverse Reaction (UAR)	An adverse reaction, the nature or severity of which is not consistent with the applicable product information (e.g., investigator's brochure for an unauthorised investigational product or summary of product characteristics for an authorised product)	

**Exempted Adverse events, Disease-Related Events and others notable events:** To be listed and defined according the study drugs safety profile and the disease under the research

**Notification Procedure:** a specific SOP focusing AE/SAE management will be drafted as SOP Working instructions for sites investigators.

The SAE Form must be completed by an investigator (a clinician named on the Signature List and Delegation of Responsibilities Log who is delegated as responsible for the participant's care), with due care being paid to the grading, causality and expectedness of the event as outlined in the related SOP. The initial report must be followed by detailed, written reports as appropriate.

The relevant concomitant medication should be documented in the SAE form. The term "relevant" refers to any treatment administered before or at the time of the event that could be related to the occurrence of the SAE, that could have a possible drug-drug interaction, that have a relevant toxicity profil for the SAE evaluation or that it is judged as important by the investigator..

The SAE Form must be e-mailed to the concerned sponsor by the applicable modality within 24h after becoming aware of the event.

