#### **Expedited reporting procedure:**

According to the applicable laws and regulations, the concerned sponsor must report all fatal and life-threatening SUSARs to the competent authorities/Ethics committees within 7 days of becoming aware of the event; other SUSARs must be reported within 15 days. In addition, any safety concern must be reported immediately to competent authorities/Ethics committees with the appropriate safety measures according to local requirements.

The concerned sponsor will submit Annual Safety Reports in the form of a Developmental Safety Update Report (DSUR) or in any requested format to Competent Authorities (Regulatory Authority and Ethics Committee).

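### Table 1 of SOP-8 tests unexpectedness by nature *and* severity for a SUSAR but by nature *or* severity for an unexpected adverse reaction, so the scope of the 7- and 15-day reports is unclear

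*Protocol*

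**What the plan says.** Table 1 (SOP-8, Definitions) has two adjacent rows that bear on expectedness.

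- SUSAR row: "A serious adverse reaction, the nature and severity of which is not consistent with the information about the medicinal product in question". The reference is the SmPC for an authorised product and the IB for any other.
- UAR row: "An adverse reaction, the nature or severity of which is not consistent with the applicable product information". The reference is again the IB or the SmPC.

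The paragraph on expedited reporting attaches both time limits to the first of these terms: "the concerned sponsor must report all fatal and life-threatening SUSARs to the competent authorities/Ethics committees within 7 days of becoming aware of the event", and "other SUSARs must be reported within 15 days". It then adds that "any safety concern must be reported immediately to competent authorities/Ethics committees with the appropriate safety measures according to local requirements". No reporting duty in SOP-8 is attached to the UAR category.

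Two further statements matter. The section opens by saying which outside definitions apply, "The definitions of the EU Directive 2001/20/EC Article 2 (and subsequent revised version CT3) based on the principles of ICH E6 (R1) GCP" together with any local requirements, and says that these are the ones set out in Table 1. The investigator completes the SAE form "with due care being paid to the grading, causality and expectedness of the event as outlined in the related SOP", and the specific SOP on AE and SAE management for sites is still to be drafted.

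**The concern.** By its name, a SUSAR is a suspected, unexpected and serious adverse reaction. One would therefore expect it to be the serious part of the UAR category, with one test of unexpectedness serving both rows. As worded, the SUSAR row can be read as the narrower test, because it names both attributes where the UAR row is satisfied by either.

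At stake is case-level expedited reporting to competent authorities and ethics committees. A reaction listed as mild that proves fatal is serious, and it is unexpected under the UAR row. On the strict reading of the SUSAR row it is not a SUSAR, because its nature is listed, and the 7-day limit does not attach to it. The definition is to be applied across many countries and sites. SOP-1 asks only for basic GCP knowledge at the centres and rules out modification of the protocol, so a conflict in the core text is hard to correct locally.

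**Working it through.** The plan states no figure here and no arithmetic applies. The check is a comparison of the two rows, followed by the reporting rule.

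**Inputs**
- SUSAR test of unexpectedness, from Table 1: nature *and* severity not consistent with the SmPC or IB.
- UAR test of unexpectedness, from Table 1: nature *or* severity not consistent with the IB or SmPC.
- Reporting trigger, from the expedited reporting paragraph: SUSAR status only, at 7 days if fatal or life-threatening and 15 days otherwise.

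**Step 1.** Take a reaction that is already judged serious and related to the product. Cross the two attributes and apply each row literally.

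| Nature unexpected? | Severity unexpected? | UAR row | SUSAR row (strict) | 7/15-day rule (strict) |
|---|---|---|---|---|
| Yes | Yes | Yes | Yes | Applies |
| No | Yes | Yes | No | Does not apply |
| Yes | No | Yes | No | Does not apply |
| No | No | No | No | Does not apply |

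**Step 2.** The rows agree in the first and last lines and disagree in the two middle lines, that is, in two of four combinations. The second line is the listed reaction at greater than listed severity. The third is the mirror case: a kind of reaction that is not listed, with a severity that is not itself inconsistent with the product information. The strict reading excludes both in the same way.

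**Step 3.** Replace *and* by *or* in the SUSAR row. The first three lines all become SUSARs, every serious UAR is a SUSAR, and the two rows agree throughout.

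**Step 4.** Look for a rule elsewhere that says which row prevails. The opening of the Definitions section invokes outside definitions but then points back to Table 1, so it returns the reader to the conflicting rows. The clause on safety concerns does not define the term, does not refer to expectedness, and is added to the 7/15-day rule without replacing it. The SOP that is to guide the judgement of expectedness is not yet written. None of these settles the conflict.

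**The case against.** The strongest reply is that the strict reading is not forced. The SUSAR row uses a singular verb and one negation over the pair. It can be read to say that nature and severity, taken together, do not match the product information, so that a mismatch in either is enough. The only row that defines *unexpected* as such is the UAR row, and a reader could sensibly take a SUSAR to be a serious UAR. The reporting paragraph also begins by deferring to applicable laws and regulations, so the duty to report does not rest on Table 1 alone.

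There are other safeguards too. Every SAE goes to the sponsor within 24 hours, whatever its expectedness. Deaths are always SAEs. Appendix 1 has the DSMC informed of SAEs as well as SUSARs. An unexpectedly fatal form of a known reaction could plausibly count as a safety concern to be reported at once.

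These points limit the consequence. A reader might infer that such cases would certainly go without expedited reports. The document does not support that: it holds only on the strict reading, and the legal sources that the Protocol invokes are not reproduced in it. A reader might also infer that SUSAR counts would not be comparable between sites. The document specifies no analysis of SUSAR counts by site, and a common operational SOP is planned, so that inference has no basis here. Nor does anything suggest that a narrower SUSAR test was chosen on purpose; this looks like a drafting inconsistency.

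The objection does not remove the contradiction. If the permissive reading is intended, the two rows should say the same thing. The 24-hour report goes to the sponsor and the DSMC is an internal safeguard. Neither is the case-level report to authorities and ethics committees that the 7- and 15-day limits govern.

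**Conclusion.** The point holds as a contradiction between two adjacent definitions. On the strict reading, serious reactions that are unexpected in exactly one respect, whether nature or severity, are UARs but not SUSARs, and so could fall outside the 7- and 15-day reports.

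Its size can be given only as a class of events: two of the four combinations of nature and severity. The document has no reaction rates, and the named products and their reference information are not shown, so no number of reports can be estimated.

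The conclusion rests on two assumptions: that the SUSAR row is applied as literally worded, and that the sponsor concerned does not go beyond it on the strength of the Directive, local law or the safety-concern clause. Where either fails, some or all of these cases would still be reported, but the text would remain inconsistent. No estimand, error rate or efficacy analysis is affected. The correction is still needed, because the wording sets the scope of mandatory safety reporting and is wrong as it stands.

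**What to change.** Reconcile the two rows of Table 1 so that one test of unexpectedness serves both. Either of these does it:

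- in the SUSAR row, replace *and* by *or* between nature and severity; or
- define a SUSAR as a serious UAR, with UAR as defined in the following row.

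The second is the more robust, since the two definitions can then no longer diverge. Carry the same wording into the SAE form and into the site working instructions while these are being drafted, so that the judgement of expectedness is made against one definition.

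The cost is one word in Table 1, or one short sentence, and possibly a few more expedited reports. Neither the data collected nor the conduct of the trial changes otherwise.

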#### **Expedited reporting procedure:**

According to the applicable laws and regulations, the concerned sponsor must report all fatal and life-threatening SUSARs to the competent authorities/Ethics committees within 7 days of becoming aware of the event; other SUSARs must be reported within 15 days. In addition, any safety concern must be reported immediately to competent authorities/Ethics committees with the appropriate safety measures according to local requirements.

The concerned sponsor will submit Annual Safety Reports in the form of a Developmental Safety Update Report (DSUR) or in any requested format to Competent Authorities (Regulatory Authority and Ethics Committee).

#### SOP-9 Reporting of protocol deviations and violations

A protocol deviation is generally considered to be a departure from the study protocol, or other study-related documents, that has not been approved by the Ethics Review Committee.

The investigator should not implement any deviation from, or changes of the protocol without agreement by the sponsor and prior review and documented approval/favourable opinion from the Ethics Review Committee of such amendment, except where:

- it is necessary to eliminate an immediate hazard(s) to trial subjects (because the protocol leaves the local doctor fully responsible for all decisions about patient care, including discontinuing study medication if considered appropriate), or
- o when the change(s) involves only logistical or administrative aspects of the trial (e.g., change in monitor(s), change of telephone number(s)

A protocol violation is a divergence from the protocol that materially (a) reduces the quality or completeness of the data, (b) makes the Informed Consent Form inaccurate, or (c) impacts a subject's safety, rights, or welfare.

When investigators are aware that a deviation is likely to take place, they may take a prior approval of the sponsor in the form of a waiver for the deviation, but when the deviation is discovered after it has taken place, and then the incident is a deviation and not a waiver.

The local monitor may grant waivers (in writing) for deviations that are not likely to impact either the data quality or safety of the subject. Since waivers are preapproved deviations, no action is necessary to be taken.

Major protocol deviations and protocol violation should be uncommon but must be reported promptly by logging into the study website.

The investigator reporting the event then enters a narrative description of the event and its seriousness that includes the trial identification number patient affected and the corrective actions taken.

